The benefits of sport and recreational activities for the disabled are well recognized from the standpoint of health and quality of life. Yet there remains a lack of options for most disabled people, especially the young. Sailing is an attractive sport that can be pursued at recreational and competitive levels. We outline a pilot therapeutic sailing program using the VSail-Access Sailing Simulator system. This program is a good fit with our current Activity Based Restorative therapy practices, and we expect that findings will add to our understanding of recovery from spinal cord injury and how to promote it. Participation in sailing by people with disabilities, particularly in small sailboats, is widely regarded as having positive outcomes on self-esteem and general health for the participants. However, a major hurdle for people with no experience of sailing, even those without disabilities, is the perception that sailing is elitist, expensive and dangerous. Real time “ride on” sailing simulators have the potential to bridge the gap between dry land and on water sailing. They provide a realistic, safe and easily supervised medium, in which non-sailors can easily and systematically learn the required skills before venturing on the water. The task of sailing on a simulator can take place under specified conditions (eg wind strength) and be taught as individual components (e.g. steering, sail trimming) in a way that is not possible on the water where there is a large number of interacting variables. The individual components can then be brought together so that the novice sailor rapidly achieves a degree of competence that would take much longer on the water. The aim of this project is to establish protocols for effective use of a simulator by people with disabilities and then to conduct a pilot trial to test two hypotheses: (1) That the use of the sailing simulator technology enables people with spinal cord injury to learn the skills required to sail on the water in a safe, non-threatening environment; (2) Teaching patients with SCI to sail using simulator technology will provide them with a safe, effective introduction to a healthy, environmentally-friendly, lifelong sport and recreation that will have measurable improvements on their physical health and psychological well-being, including their confidence (self-esteem), morale, and optimism about the future. In this pilot trial 20 subjects with spinal cord injury will be recruited, assessed medically, and with questionnaires to establish baselines for evaluation of quality of life and self-esteem. All subjects will follow a course of instruction leading to mastery of basic sailing techniques such that at the end of the course the subjects will be able to perform a series of standard sailing maneuvers and navigate competently a triangular racecourse on the simulator’s display in 12 knots of wind within a preset time. The deliverables will be a detailed protocol for the use of sailing simulators to prepare people with disabilities to start sailing on the water. A secondary deliverable will be a structured protocol for use by sailing centers working with people with disabilities who enter sailing by direct participation on the water. Once the participants have completed the 12 week course they will have the opportunity to sail on the water with the assistance of the Downtown Sailing Club (DSC), Baltimore; however, this is not part of the formal pilot trial, which is aimed primarily at determining the optimum use of a sailing simulator for training purposes. The information from this pilot trial will be used to formulate a future more comprehensive study, which will include a major on water component in collaboration with the Downtown Sailing Club.

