a. Study design, including the sequence and timing of study procedures (distinguish research procedures from those that are part of routine care).

This is a within subject pilot study that plans to enroll 20 chronic (more than 6 months) SCI patients as per recruitment matrix in Table 1. This pilot study will provide preliminary evidence with respect to both Hypothesis 1 and Hypothesis 2 (see above). Organization of a larger trial is planned, the detail design of which will depend upon the outcomes from this study, and subjects will be recruited from individuals already undergoing rehabilitative interventions at the International Center for Spinal Cord Injury (ICSCI) at the Kennedy Krieger Institute and nearby military medical centers (Walter Reed, Baltimore VA). In addition to their already prescribed rehabilitation regimen, the eligible subjects will engage in a virtual reality sailing program (VSail) once a week, 1h/session for 12 weeks. The subjects will be assessed using a battery of physical and neurological indicators before starting the training (baseline), after 6 weeks and 12 weeks of training, and at 6 and 12 months following the completion of the training. During each training visit outcomes will be assessed by the trainer. The study timeline is found in Figure 1.

	High Tetra (C1-C5)	Low Tetra (C6-C8)	High Para (T1-T6)	Low Para (T7-T12)	Coda Equina (L1-S1)
Motor Complete (A-B)	2	2	2	2	2
Motor Incomplete (C-D)	2	2	2	2	2

Table 1: Recruitment Matrix

[figure not shown]

Figure 1: Study Time Line

All activities will be conducted at Kennedy Krieger Institute and are supervised by the Principal Investigator.

(1) Study Intervention:

All activities will be conducted at Kennedy Krieger Institute by a VSail trainer.

While undergoing the virtual sailing training, the subjects will use a VSail-Access simulator (Virtual Sailing, Melbourne, Australia). The VSail simulator will be set in the Access Dinghy mode. The VSail sailing parameters will be set to the subjects skill set and progression in the training program: wind speed from minimum (8 knots) to moderate strength (14 knots), pneumatic rams (simulating the heeling of the hull) on or off.

The subjects will be transferred to the VSail cockpit and secured. Following the trainer's instruction, the subject will sail the simulator around virtual courses displayed on a computer screen, using a joystick to control the rudder angle and a mainsheet to control the set of the sail.

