(i) Sailing Ability Questionnaire: This is a routine test performed for people involved in a training program. This questionnaire will assess the subject's views about sailing, as well as the subject's perceived sailing abilities. This questionnaire will be used for all subjects.

(j) Cardio-Vascular Monitoring: This is a routine test performed for people undergoing a cardio-vascular type exercise. This test will be performed on all subjects. The following vital sign will be recorded:

- Fatigue as per RPE.
- Blood pressure and heart rate with any sign or symptom of autonomic dysreflexia (AD) (manifested as pilo-erection, sudden and profuse sweating above injury level, facial flushing, intense head/neck tingling, headache) or signs of orthostatic hypotension (dizziness, light headedness, palpitations, sudden vision loss, profuse sweating).

(k) Sailing Score: This is a routine function of the VSail-Access simulator. The score will be based on the ability to perform specific sailing maneuvers (steering predetermined courses, sail trimming, tacking, gybing, mark rounding), and the ability to navigate a simple course around marker buoys (triangular configuration) on the computer screen within a predetermined time. This test will be performed on all subjects.

(l) Weekly Diary: This is a routine test performed for people in a clinical study. A weekly diary will be kept by the subject. The following events will be recorded: change in medical status, change in medication, change in prescribed rehab program. The study coordinator will review the diary with the subject every week. This will be done for all subjects.

(m) Follow-up Questionnaire: This is a routine test performed for people involved in a training program. This questionnaire will assess the subject's views about sailing on the water after been in the VSail training program, as well as the subject's perceived sailing abilities.. This questionnaire will be used for all subjects.

b. Study duration and number of study visits required of research participants.

The study will last one (1) year, with an active training phase of 12 weeks. The subjects will continue their already prescribed treatment rehabilitation regimen, and attend one hour session of virtual reality sailing once a week for 12 weeks. They will return at 6 and 12 months to be assessed. The study timeline is found in Figure 1 and the data collection schedule in Table 2.

	Initial	Training	Weekly	6 Weeks	12 Weeks	6 Months	12 Months

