	2 hours	1 hours	10 minutes	2 hours	2 hours	10 minutes	10 minutes
Vital Signs	√			√	√		
PFTs	√			√	√		
ASIA	√			√	√		
SCI QL-23	√			√	√		
VR-36	√			√	√		
Functional Reach	√			√	√		
Trunk	√			√	√		
Grasp/Pinch	√			√	√		
Sailing Ability	√				√		
Cardio-Vascular		√					
Sailing Score		√					

Version: 2
 Date: January 13th 2015
 Principal Investigator: [name].
Application Number: NA_00044093

Diary				√				
Follow-up Q							√	√

Table 2: Data Collection Schedule

The following assessments will be performed at the Initial, and 12 Week visits:

- (a) Vital Signs (about 5 mins)
- (b) Pulmonary Function Test (about 5 mins)
- (c) ASIA (60 mins)
- (d) SCI QL-23 (about 10 mins)
- (e) VR-36 (about 10 mins)
- (f) Functional Reach Test (about 5 mins)
- (g) Level of Trunk Activation (about 5 mins)
- (h) Grasp/Pinch test (about 5 mins)
- (i) Sailing Ability Questionnaire (about 5 mins)

The following assessments will be performed at the 6 Week visits:

- (a) Vital Signs (about 5 mins)
- (b) Pulmonary Function Test (about 5 mins)
- (c) ASIA (60 mins)
- (d) SCI QL-23 (about 10 mins)
- (e) VR-36 (about 10 mins)
- (f) Functional Reach Test (about 5 mins)
- (g) Level of Trunk Activation (about 5 mins)
- (h) Grasp/Pinch test (about 5 mins)

The following assessments will be performed at all VSail training Visits:

- (j) Cardio-Vascular Monitoring (about additional 5 minutes to VSail session)
- (k) Sailing Score (about 5 minutes included in VSail session)

The following assessments will be performed weekly during the training:

- (l) Weekly Diary review (about 10 minutes), once a week only

The following assessments will be performed at the 6 Month and 12 Month visits:

- (m) Follow-up Questionnaire (about 10 mins)

c. Blinding, including justification for blinding or not blinding the trial, if applicable.

Not Applicable.

d. Justification of why participants will not receive routine care or will have current therapy stopped.

All subjects will continue to consistently perform their usual (“baseline”) amount of physical activity throughout the study, including clinic and home exercise program. “Baseline” activity is defined as amount of physical activity performed for at least 1 month prior to enrollment. Routine care will not be interrupted.

e. Justification for inclusion of a placebo or non-treatment group.

Not Applicable.

Version: 2
Date: January 13th 2015
Principal Investigator: [name].
Application Number: NA_00044093

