- i. Active sailor.
- j. Active drug or alcohol use or dependence that, in the opinion of the site investigator, would interfere with adherence to study requirements.

4. Drugs/ Substances/ Devices

a. The rationale for choosing the drug and dose or for choosing the device to be used.

The VSail-Access simulator (Virtual Sailing, Melbourne, Australia) is the first sailing simulator available for people with disabilities.

The VSail simulator is a generic sailboat cockpit powered by a pneumatic ram and custom designed software. The sailor sails the simulator around virtual courses displayed on a computer screen or overhead display in the same way as a real sailboat on water (a tiller to control the rudder angle, a mainsheet to control the set of the sail and body position to control heeling of the hull). Electronic sensors provide real time feedback to match the movements of the virtual sailboat displayed on the screen with those of the simulator. Sailors can select wind strength and conditions to suit their ability. The VSail-Access simulator is a variation on the VSail where the cockpit is fitted with a seat based on the design used for Access dinghies (<http://accessdinghy.org>).

b. Justification and safety information if FDA approved drugs will be administered for non-FDA approved indications or if doses or routes of administration or participant populations are changed.

Not applicable.

Version: 2
Date: January 13th 2015
Principal Investigator: [name].
Application Number: NA_00044093

c. Justification and safety information if non-FDA approved drugs without an IND will be administered.

Not applicable.

5. Study Statistics

a. Primary outcome variable.

(1) Ability to sail:

- (a) standard maneuvers: ability to perform specific sailing maneuvers (steering predetermined courses, sail trimming, tacking, gybing, mark rounding).
- (b) Ability to navigate a simple course around marker buoys (triangular configuration) on the computer screen within preset time.

(2) Quantitative health, welfare, self esteem and quality of life survey.

b. Secondary outcome variables.

- (1) ASIA (American Spinal Injury Association) scoring.
- (2) Cardio vascular health (pulmonary function test, vital signs).
- (3) Trunk control (functional testing of reach, level of trunk muscle activation).
- (4) Grip and pinch strength.

c. Statistical plan including sample size justification and interim data analysis.

This is a pilot study. No statistical analysis is planned.

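### Primary outcome 5.a(1)(b) records only whether an unstated time limit was met; completion time, from a run that must be timed anyway, should be added under standard conditions

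*Protocol*

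**What the plan says.** Section 5.a lists two primary outcomes. The first, ability to sail, has two parts: (a) standard maneuvers and (b) "Ability to navigate a simple course around marker buoys (triangular configuration) on the computer screen within preset time". The second is "Quantitative health, welfare, self esteem and quality of life survey".

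The same threshold appears twice more. The opening summary sets the end-of-course goal as being able to "navigate competently a triangular racecourse on the simulator’s display in 12 knots of wind within a preset time". Section 3.a(2)(k) bases the Sailing Score partly on "the ability to navigate a simple course around marker buoys (triangular configuration) on the computer screen within a predetermined time". None of the three places gives the limit, and none names elapsed time as something to report. The Sailing Score has no stated scale, range or weighting.

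The Sailing Score is taken at every training visit: section 3.b introduces it with "The following assessments will be performed at all VSail training Visits". One session a week for 12 weeks gives up to 12 scores per subject. Section 3.a lets wind vary from 8 to 14 knots during training, and the pneumatic rams be on or off, according to skill and progress.

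Section 5.c states: "This is a pilot study. No statistical analysis is planned". On the use of the results, section 3.a says: "Organization of a larger trial is planned, the detail design of which will depend upon the outcomes from this study".

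**The concern.** A threshold on time keeps one bit of a measured quantity. A subject who just makes the limit and one who beats it easily count the same, as do one who narrowly misses it and one who never finishes.

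The design pushes the binary outcome towards its extremes. Active sailors are excluded, so most subjects are likely to miss the limit early on, and the course is meant to bring them to mastery by week 12. If nearly all 20 pass at the end, the pass rate says little about how much was learned, who learned slowly, or how variable performance is. It also depends wholly on a limit that the protocol does not state, whereas recorded times could be read against any limit.

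What is at stake is estimation and planning, which is what a pilot is for. Completion times that are not recorded cannot be recovered later.

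**Working it through.** **Inputs from the protocol.** N = 20, from the recruitment matrix in Table 1: 2 severity rows × 5 level columns × 2 subjects = 20, which reproduces the stated enrolment. There is no alpha, power, effect size, SD, expected pass rate or time limit to reproduce.

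**Assumptions.** Pass rate p, ranged because the protocol gives none. Completion time normal on some scale, for example after a log.

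**1. Pass/fail against fully observed times.** With z the normal quantile of p and φ the normal density, the share of information about the mean that is kept is φ(z)² / [p(1 − p)].

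- p = 0.50: 0.3989² / 0.25 = 0.637, worth 12.7 of 20 subjects; loss 36%.
- p = 0.80: 0.2800² / 0.16 = 0.490, worth 9.8; loss 51%.
- p = 0.90: 0.1755² / 0.09 = 0.342, worth 6.8; loss 66%.
- p = 0.95: 0.224, worth 4.5; loss 78%.

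The formula is symmetric in p and 1 − p, so two thirds is not an upper bound.

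**2. Pass/fail against times censored at the limit.** If every run beyond the limit is censored there, the information available (SD known, SD = 1) is p − zφ(z) + φ(z)² / (1 − p). Pass/fail keeps the following share of it:

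| Pass rate | Pass/fail | Censored times | Share kept | Loss |
|---|---|---|---|---|
| 10% | 0.342 | 0.359 | 95% | 5% |
| 20% | 0.490 | 0.534 | 92% | 8% |
| 50% | 0.637 | 0.818 | 78% | 22% |
| 80% | 0.490 | 0.956 | 51% | 49% |
| 90% | 0.342 | 0.983 | 35% | 65% |

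So the loss is about half to two thirds at pass rates of 80% to 90% by either comparison. At 10% to 20%, censoring at the limit recovers almost nothing; more is gained there only by letting slow runs finish and recording their times.

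**3. Precision with 20 subjects.** Wilson 95% limits for 16/20 are 58% to 92%, and for 20/20 they are 84% to 100%. An SD estimated from 20 uncensored times has 95% limits of √(19/χ²) with 19 df, that is 0.76 to 1.46 times the estimate: rough, but usable for planning.

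**4. Illustration for a later trial.** Take two arms, two-sided 0.05, 80% power, and an assumed effect of 0.5 SD. With times, n per arm = 2(1.960 + 0.842)² / 0.5² = 62.8, rounded up to 63. With pass/fail, the second pass rate is Φ(z + 0.5):

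- 50% against 69.1%: 102 per arm.
- 80% against 91.0%: 160 per arm.
- 90% against 96.3%: 256 per arm.

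**The case against.** The strongest reply is that a threshold suits the question. Hypothesis 1 asks whether people learn the skills required, the opening summary defines a competence standard, and the number reaching that standard answers the hypothesis more directly than seconds do. This stands, and it is why the proportion should stay.

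Second, a reader might infer that elapsed time is thrown away. The protocol does not say so. Recording it is neither stated nor ruled out, and the Sailing Score, whose scale is not described, may be graded. What can be said is that outcome 5.a(1)(b) is worded only as a threshold.

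Third, a reader might infer that the pilot leaves no variance estimate at all for the larger trial. That is too strong. A pass rate has a binomial variance, the Sailing Score is repeated weekly, and primary outcome (2) is quantitative. What is not provided for is an SD of completion time. Nor does section 3.a name such an SD as an aim.

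Fourth, no test is planned, so no stated power is lost, and details of summary may sit in an analysis plan that is not shown. That is fair as far as analysis goes, but the definition of the primary outcome is fixed in section 5.a itself.

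Fifth, training conditions vary, so times from ordinary sessions would mix learning with wind and ram settings. This stands, and the fix has to deal with it.

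**Conclusion.** The point holds as a matter of outcome definition and lost precision; it does not invalidate the pilot. Outcome 5.a(1)(b) is a threshold at an unstated limit, and the protocol does not name completion time as an outcome although the run must be timed.

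At end-of-course pass rates of 80% to 90%, about half to two thirds of the information in the times is lost. That range rests on assumed pass rates and roughly normal times, neither of which the protocol supplies, so it should not be quoted as a fixed property of the design. A reader might also extend the large loss to the early sessions. Against times censored at the limit it is only 5% to 8% at pass rates of 10% to 20%, and 22% at 50%.

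The change is worth making because it is cheap and the missing data could not be reconstructed afterwards.

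**What to change.** In section 5.a(1)(b):

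- Keep the proportion finishing within the limit as the competence criterion, and state the limit.
- Add actual completion time in seconds, including for runs that finish after the limit. Censor only runs that are not finished.
- Take the timed run under one standard simulator setting, for example the 12 knots already named in the opening summary, with the ram setting fixed.
- Summarise time as a median or a within-subject change, with an interval.

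In section 3.a(2)(k), state the scale of the Sailing Score and whether elapsed time enters it.

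The cost is one extra data field, a rule for handling censored runs, and a standardised test run so that times are comparable despite the varying training settings. Letting slow runs finish may also take some session time.
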